6.7.5 Treatment for Reactions During the Up-dosing Period: Dose Adjustment

If a dose or dose level is assessed *as not tolerated*, the action taken will depend on the type and severity of the dose-related reaction and the investigator's clinical judgement. The following possible actions are at the investigator's disposal and are considered in greater detail in subsequent sections (Section 6.7.5.1, Section 6.7.5.2, and Section 6.7.5.3, and Figure 6-2):

- Dosing the subject under medical supervision in the CRC this is encouraged whenever there is question as to the tolerability of a dose level. It may be performed at the current dose level or at a reduced dose level, if there is already a high index of suspicion that the current dose level has not been tolerated.
- Holding dose level at current level for an additional 1 to 2 weeks before attempting dose escalation this may be done at the discretion of the investigator if there is concern that the current dose level has not been sufficiently well tolerated to attempt up-doing to the next dose level.
- Reducing dose by 1 or 2 dose levels and maintaining the reduced dose level for at least a 2- to 4-week period before attempting dose re-escalation – Generally, this should be the

action taken when a dose that has been observed in the CRC is assessed as not tolerated, if a dose elicits moderately severe symptoms, if a single dose of epinephrine has been administered to treat a dosing reaction, or if the investigator is convinced of the intolerability of the current dose level. In short, it should be considered the default action whenever a dose or dose level is assessed *as not tolerated*.

- Reducing dose level for less than the usual 2-week period this may be instituted as treatment for an intercurrent AE, to aid the investigator in determining if a dose level is or is not tolerated, or if a pattern of decreased study product tolerability during menses is discerned. The level of the reduction in dose, ranging from a 1-step reduction to a 50% reduction will be at the investigator's discretion, based on clinical judgement. The manner in which dose escalation may resume will depend on the level and the duration of the dose reduction.
- Temporarily withholding study product dosing this may be instituted as treatment for an intercurrent AE or to aid the investigator in determining if a dose level is or is not tolerated, but the duration of withholding study product may not exceed 14 consecutive days, or the subject will be discontinued from the study. The manner in which dosing may resume after withholding dosing of study product depends on the duration for which dosing was withheld.
- Reducing dose by 2 dose levels and maintaining the reduced dose level for at least 6 weeks – continuing dosing at a reduced dose level for at least 6 weeks prior to attempting re-escalation is mandatory if 2 doses of epinephrine are given to treat a single AE.
- Stopping dosing and discontinuing the subject early from the study this is an option that the subject may elect at any time and for any reason. The investigator must discontinue the subject from further dosing and continuation in the trial under circumstances that could jeopardize the health of the subject or the integrity of the trial.

6.7.5.1 Reactions to In-Clinic Dosing

If symptoms arise in the clinic after up-dosing, the investigator is to determine whether or not the dose was tolerated (Section 6.7.3). The process algorithm for continued dosing after dose-related symptoms occur is described below and shown in Figure 6-2.

If a subject has a dose escalation in the CRC without symptoms, the action should be to continue, per protocol, with daily home dosing at the tolerated dose level and return to the CRC for the next scheduled dose escalation visit 2 weeks later.

If the subject experiences only *oral/pharyngeal pruritus* following the administration of the first dose at a new dose level, the dose will generally be *assessed as tolerated*, and the same dose can be repeated the next day at home and continued throughout the 2-week home-dosing interval, unless other symptoms begin to develop (see below).

If other *mild symptoms* occur with the first dose at a new dose level and the dose is *assessed as not tolerated*, the action taken should be to have the subject return to the CRC the next day for dosing at the last tolerated dose (ie, a 1-step dose reduction) under medical supervision (if the subject is unable to return to the CRC on the day specified, the investigator may initiate an

CONFIDENTIAL

approximate 1 dose-level reduction at home, with the subject coming to the CRC at the earliest date possible). If the reduced dose is *assessed as tolerated*, the subject is to continue on that daily home dose for the ensuing 2 weeks. (Section 6.7.5.2 for actions to be taken in the event that symptoms develop during home-dosing.) If the reduced dose is again *assessed as not tolerated*, the subject is to return to the CRC the next day for supervised dosing at a 1- or 2-step reduction in dose (per investigator judgment, based on severity of reaction). If this further reduced dose is *assessed as tolerated*, the subject will continue at that dose level for daily home-dosing over the ensuing 2 weeks. If, however, the reduced dose is *assessed as not tolerated*, the subject is to be considered an escalation failure nonresponder.

If *mild symptoms* occur with the first dose at a new dose level and the dose is *assessed as tolerated*, the action taken should be to repeat the same dose the next day. It is advised that the repeat (next day's) dose be administered in the CRC, but it may be given at home, at the investigating physician's discretion. If the second dose at the new (increased) dose level is tolerated without symptoms, then the subject is to continue on that dose level for the requisite 2 weeks and return to the CRC for up-dosing at the next scheduled visit. If the dose again causes mild symptoms, but is *assessed as tolerated*, the subject may continue at that dose level or return to the last tolerated dose (at the investigator's discretion) and continue dosing at home for the next 2 weeks at the investigator-determined dose level. (Section 6.7.5.2 for actions to be taken in the event that symptoms develop during home-dosing.) If, following the first dose at a new dose level, the second dose at the new (increased) dose level is again accompanied by mild symptoms, but is *assessed as not tolerated*, the procedures outlined in the paragraph above should be followed.

For specific questions related to dose-escalation or continuation of the same dose that are not answered in the above protocol, the Medical Monitor will be available for consultation.

6.7.5.2 Reactions to Dosing at Home

With the occurrence of symptoms of an acute reaction to study product after home-dosing, or any acute allergic reaction, subjects/parents or guardians are instructed to call the study site. The investigator must then determine whether or not the dose was tolerated (Section 6.7.3). Because of the reduced reliability inherent in the second-hand reporting of symptoms, investigators are strongly encouraged to have subjects return to the clinic to undergo dosing under direct observation whenever acute allergic symptoms associated with dosing are reported.

When symptoms of a dose-related allergic reaction are reported during the course of daily home-dosing, the investigator must assess the severity of the reaction and whether the dose associated with the reaction was tolerated. The appropriate intervention will depend on the type and severity of symptoms (Section 6.7.5.2 and Figure 6-2).

In general, moderate or severe symptoms will be considered clinically significant, and any dose eliciting such symptoms *assessed as not tolerated*; however, mild symptoms may also be considered clinically significant, eg, if affecting multiple organ systems, increasing in intensity, occurring with increasing frequency, or affecting a larger area over time, and *assessed as not tolerated*. Whenever there is question as to the clinical significance of mild signs or symptoms, the investigator should have the subject return to the CRC for observed dosing under medical supervision.

For home-doses *assessed as not tolerated* on the basis of acute dose-related symptoms, the same procedures described in **Section 6.7.5**, above, for adjusting up-dosing should be followed.

The recurrence of mild symptoms over the course of several days of home-dosing should suggest that the dose level is not tolerated, even if each individual occurrence of symptoms could be assessed as tolerated on the basis of the criteria listed above. In this circumstance, investigator judgment will be required to determine the best course of action with the possible actions being the following:

- Continue with daily home dosing at the current dose level
- Continue the same daily dose for the rest of the 2-week interval, with the dose split into 2 fractional doses given 8 to 12 hours apart (the 2 fractional doses need not be equal)
- Return to the CRC for repeat dosing at the current dose level under direct observation to confirm whether or not the dose level is tolerated

- Return to the CRC for dosing of a previously tolerated dose level, either a 1- or 2-step reduction (per investigator judgment, based on severity of reaction) and follow the procedures described in Section 6.7.5.2 above
- Institute the 4-week hiatus from dosing, with resumption of dosing at the 3 mg/d dose level, as permitted for recurrent GI symptoms occurring at or before the 20 mg, as described in Section 6.7.3.2.
- Discontinuation of dosing

Any subject who discontinues build-up dosing due to severe or repeated allergic reactions to study product should have his/her mechanistic blood draw and CBC (Section 8) at, or as nearly as possible to, the time of the last dose and no later than at their Early Discontinuation Visit.

[figure not shown]

Figure 6-2: Schematic for Up-dosing Period Dose Adjustment

6.7.5.3 Dose Adjustment in Response to Adverse Events

At the investigating physician's discretion, temporary dose reductions, ranging from a 1-step decrement (ie, to the previous dose) to approximately half of the current dose level (to the nearest feasible available whole dose), can be instituted as part of the treatment regimen for an intercurrent AE. Also, if a pattern of decreased tolerability of study product during menses is discerned, then a temporary dose reduction can be instituted during this time. Temporary dose reductions for intercurrent AEs may be instituted as follows:

- For dose reductions of ≤ 4 consecutive days, whether dose re-escalation is to occur at home or in the CRC is at the investigator's discretion. If the reduction in dose is maintained for ≤ 4 consecutive days, then the prereduction dose level may be resumed, with the biweekly escalation schedule kept unaltered.
- If a reduction in dose is maintained for 5 to 7 consecutive days, then the subject is to return to the CRC to undergo dosing under medical supervision. At the investigator's discretion, the prereduction dose level may be resumed or dosing may continue at the reduced dose level. The biweekly escalation should be reset so that the subject receives at least 2 consecutive weeks of treatment at the dose level assigned (either the reduced or the prereduction dose level).
- If a reduction in dose is maintained for 8 to 14 consecutive days, then the next escalation attempted must be conducted in the clinic, and it should only be to 1 dose level above the reduced dose. If the escalation is successful, the subject should continue home-dosing for a minimum of 2 weeks, with his or her biweekly escalation schedule reset as necessary.

Doses of study product may also be withheld at the investigator's discretion, in response to an intercurrent AE. Doses withheld as part of the treatment for an AE constitute a special category of missed peanut OIT doses (Section 6.8).

6.7.6 Treatment for Reactions During the Up-dosing Period: Pharmacological and Supportive Treatments

Treatment of acute reactions should be with either an antihistamine and/or epinephrine, along with IV fluids, a beta-agonist (eg, albuterol, by inhaler or nebulizer), oxygen, and/or glucocorticosteroids, as indicated.

Many mild acute allergic reactions can be transient and self-limiting, requiring no therapeutic intervention. Others, however, may require treatment. Generally, for mild symptoms requiring treatment, the subject should receive antihistamines.

Acute allergic reactions manifesting with moderate symptoms will generally require therapeutic intervention, although some, even moderate, symptoms may on rare occasion be so transient as to require no specific treatment. Generally, for moderate symptoms requiring treatment, the subjects should receive antihistamines and/or epinephrine, as indicated. If there is uncertainty as to the severity of the reaction, administering epinephrine would be considered the most appropriate course of action.

Generally, severe symptoms will require treatment with epinephrine at a minimum. If severe symptoms that qualify as stage 3 anaphylaxis (defined in **Appendix 3**) occur at any time, dosing with study product will stop and the subject will be discontinued from the study as an escalation failure nonresponder.

Antihistamines

If a subject receives antihistamines only, the dose escalation can be continued. If symptoms during a build-up day require administration of more than 2 doses of an antihistamine or of an antihistamine in combination with other medications (except epinephrine), there should be a dose reduction of 1 or 2 dose levels, with the next dose given in the CRC. If epinephrine is administered, then a different course of action is to be taken (see below).

Epinephrine - General

Any reaction to study product (in clinic or at home) that requires more than two doses of epinephrine will halt all further dosing of study product for the individual. The subject will be asked to return to the CRC 14 days following the last dose of study product to undergo an Early Discontinuation Visit (Section 6.5).

Epinephrine - Clinic

If a single administration of epinephrine is required during, or after, a dose-escalation in the clinic, no further dosing of study product is to occur at that visit. The next dose of study product is to be reduced by two dose levels and administered in the CRC, but biweekly dose escalation should continue.

If a single administration of epinephrine is required a second consecutive time during, or after, 1 escalation attempt, the dose should be reduced by two dose levels, and the subject continued at that dose level for 6 to 8 weeks. After 6 to 8 weeks at the reduced dose, an escalation attempt may be tried in clinic.

If a single administration of epinephrine is required a third consecutive time during an escalation attempt, no further dosing should be attempted. Dosing in these subjects will be discontinued. They will be asked to return to the CRC 14 days following their last dose of study product to undergo an Early Discontinuation Visit (Section 6.5).

Epinephrine - Home

If a single administration of epinephrine is given during dosing at home, this epinephrine use is not counted as 1 of the uses described above, unless severe anaphylaxis is assessed to have occurred at home. Administration of epinephrine outside of the clinic should be followed immediately by the subject being taken to the nearest emergency department. The subject should return to clinic for an observed dose under medical supervision prior to resuming any dosing at home.

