At a minimum, subjects must be observed for 90 min. $(1\frac{1}{2} \text{ hours})$ after completion of dose escalation, with vital sign measurements and assessment for signs and symptoms of allergic reaction performed every 30 minutes. Any signs or symptoms of allergic reaction will be recorded in the CRF on the appropriate Dosing Symptom/AE form.

If Day-1 dose escalation is completed with no symptoms detected after 1½ hours of post-dose observation, the subject may be sent home from the CRC. If the subject exhibited mild symptoms, the duration of the observation period should be extended to a minimum of 1 hour after resolution of the symptoms. For moderate symptoms, the observation period should be extended to a minimum of 2 hours after resolution of the symptoms. And for severe symptoms, the subject should be observed for a minimum of 3 hours after resolution of the symptoms, either at the CRC or an emergency facility, as appropriate.

Any subject deemed to have severe symptoms that include hypoxia, hypotension, or change in mental status, stage 3 anaphylaxis defined in **Appendix 3**, or who receives intensive therapy (to be determined by the investigator, but may include such interventions as IV epinephrine, intubation, or admission to an intensive care unit) for an allergic reaction at any time should be discussed with the Medical Monitor and discontinued from the study.

If dose-limiting symptoms occur at or before the 3 mg single dose, there will be no further dosing of study product, and the subject will be classified as an escalation failure and a nonresponder for the purpose of primary and key secondary analyses. The subject will be asked to return to the CRC 14 days following the last dose of study product to undergo an Early Discontinuation Visit (Section 6.5). The subject will continue to be monitored for safety until the Early Discontinuation Visit is completed or any ongoing AEs are resolved, whichever is longer.

If no dose-limiting symptoms occur during Day-1 dose escalation, or if dose-limiting symptoms occur only with the 6 mg single dose, the subject is to return to the CRC on Day-2 to confirm the tolerability of a single 3 mg dose of study product.

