Any subject deemed to have severe symptoms that include hypoxia, hypotension, or change in mental status (stage 3 anaphylaxis defined in **Appendix 3**), or who receives intensive therapy (to be determined by the investigator, but may include such interventions as IV epinephrine, intubation, or admission to an intensive care unit) for an allergic reaction at any time should be discussed with the Medical Monitor and discontinued from the study.

If dose-limiting symptoms occur on Day -2, there will be no further dosing of study product, and the subject will be classified as an escalation failure and a nonresponder for the purpose of primary and key secondary analyses. The subject will be asked to return to the CRC 14 days following the last dose of study product to undergo an Early Discontinuation Visit (Section 6.5). The subject will continue to be monitored for safety until the Early Discontinuation Visit is completed or any ongoing AEs are resolved, whichever is longer.

Those subjects who tolerate the single 3 mg dose of study product on Day -2 will be dispensed a 2-week supply of study product at the 3 mg/d dose level. They will be instructed to continue daily oral dosing at home, starting the following day (Study Day -3), and to continue daily home dosing at that dose level for 2 weeks until next escalation.

On Day -3, the site is to make telephone contact with the subject/subject's parent or guardian to enquire if any AEs (including allergic symptoms) occurred subsequent to the subject leaving the clinic, and to provide assistance in recording of, and responding to, any such events.

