At a minimum, subjects must be observed for 1½ hours after dose administration, with vital sign measurements and assessment for signs and symptoms of allergic reaction performed every 30 minutes. Any signs or symptoms of allergic reaction will be recorded in the CRF on the appropriate Dosing Symptom/AE form.

If up-dosing is completed with no symptoms detected after 1½ hours of post-dose observation, the subject may be sent home from the CRC. If the subject exhibited mild symptoms, the duration of the observation period should be extended to a minimum of 1 hour after resolution of the symptoms. For moderate symptoms, the observation period should be extended to a minimum of 2 hours after resolution of the symptoms. And for severe symptoms, the subject should be observed for a minimum of 3 hours after resolution of the symptoms, either at the CRC or an emergency facility, as appropriate.

Any subject deemed to have severe symptoms that include hypoxia, hypotension, or change in mental status (stage 3 anaphylaxis defined in **Appendix 3**), or who receives intensive therapy (to be determined by the investigator, but may include such interventions as IV epinephrine,

intubation, or admission to an intensive care unit) for an allergic reaction at any time should be discussed with the Medical Monitor and discontinued from the study.

On the day following in-clinic up-dosing, the site is to make telephone contact with the subject/subject's parent or guardian to enquire if any AEs (including allergic symptoms) occurred subsequent to the subject leaving the clinic, and to provide assistance in the recording of any such events in the diary.

A dose escalation attempt may be postponed 1 to 2 weeks if, in the clinical judgment of the investigator, the current dose level has not been sufficiently well tolerated to proceed to the next dose level. Further, if an investigator suspects that a subject has not tolerated, or is not tolerating, his or her current dose level, the investigator should have the subject return to the clinic to determine whether a dose reduction is warranted, and if so, the magnitude of the reduction. Guidelines for setting the new, lower, dose are outlined in Section 6.7.5, with the dose adjustment depending on the severity of the dose-related symptoms.

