6.7.3 Assessment of the Tolerability of a Dose Level

6.7.3.1 Assessment of Acute Symptoms Occurring after Dosing

The assessment of the tolerability of a single dose forms the foundation for assessing the tolerability of a dose level during home-dosing when acute symptoms arise in close temporal succession to dosing. With the report of moderate or severe symptoms occurring during home-dosing, the dose level should be considered not tolerated and the subject brought to the clinic the day after the emergence of such symptoms for administration of the next dose of study product under medical supervision. If a dose administered at home is suspected to have been not tolerated, even on the basis of mild symptoms, the subject should also return to the CRC for dosing under medical supervision.

The recurrence of a mild symptom or symptoms over the course of several days of home-dosing should suggest that the dose level is not tolerated, even if each individual occurrence of symptoms could be assessed as tolerated on the basis of the criteria listed above. If the investigational site is notified of mild dose-related symptoms on 4 or more occasions during a single week, the subject should be brought to the CRC for dosing under direct observation for assessment of the tolerability of the dose level. If mild dose-related symptoms are noted on 7 or more occasions during a 2-week dosing interval at a given dose level, that dose level should be considered not tolerated and appropriate action taken (Section 6.7.5.2).

Because of the reduced reliability inherent in the second-hand reporting of symptoms, investigators are strongly encouraged to have subjects return to the clinic to undergo dosing under direct observation whenever acute allergic symptoms associated with dosing are reported.

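### Protocol 6.7.6 (Epinephrine - Home), 6.7.3.1 and 6.7.5.1 describe further dosing after severe reactions without deferring to the stage 3 anaphylaxis stop rule that governs them

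*Protocol*

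**What the plan says.** The stop rule comes early in protocol section 6.7.6, ahead of the paragraphs on individual drugs. If severe symptoms that meet the Appendix 3 definition of stage 3 anaphylaxis "occur at any time, dosing with study product will stop and the subject will be discontinued from the study as an escalation failure nonresponder". Section 6.3.2 agrees for up-dosing: a subject with severe symptoms of that kind, or one given intensive therapy, "for an allergic reaction at any time should be discussed with the Medical Monitor and discontinued from the study". Sections 6.3.1.1 and 6.3.1.2 say the same for the two initial escalation days. Section 4.3.1 requires termination of allergen exposure for CoFAR Grade 4 reactions, including anaphylaxis with hypotension or neurological compromise, and for Grade 3 reactions.

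The dosing instructions at issue are these:

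- **6.7.6, Epinephrine - Clinic.** After one epinephrine administration, the "next dose of study product is to be reduced by two dose levels and administered in the CRC, but biweekly dose escalation should continue". A second consecutive use brings another two-level reduction, held for 6 to 8 weeks. A third consecutive use ends dosing.
- **6.7.6, Epinephrine - Home.** After a single home administration, "this epinephrine use is not counted as 1 of the uses described above, unless severe anaphylaxis is assessed to have occurred at home". The subject goes to an emergency department, and then: "The subject should return to clinic for an observed dose under medical supervision prior to resuming any dosing at home".
- **6.7.3.1.** A subject with moderate or severe symptoms during home dosing is to be "brought to the clinic the day after the emergence of such symptoms for administration of the next dose of study product", under medical supervision.
- **6.7.5.1.** After severe symptoms in clinic, the investigator and the Medical Monitor decide whether the subject continues. If so, a dose two steps lower follows the next day. Section 6.7.5.2 sends home doses that were not tolerated to the procedures of 6.7.5.

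Section 6.7.7 applies the same rules in the Maintenance Period.

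**The concern.** Take a subject who has stage 3 anaphylaxis after a home dose and receives one epinephrine injection. The stop rule says that treatment is over. The paragraph that a site would naturally open after home epinephrine does not say so. It talks of counting the use and of an observed dose in clinic, and 6.7.3.1 asks for that next dose on the following day. A site that read only those lines could give allergen again to a participant, often a child, who had just had hypoxia, hypotension or neurological compromise. What is at stake is participant safety in a rare situation.

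**Working it through.** No arithmetic applies. The check is to follow one event, stage 3 anaphylaxis after a home dose treated with one injection, through each instruction.

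1. **What severe anaphylaxis means.** Section 7.6 grades anaphylaxis by the Appendix 3 system, where stage 3 is the stage labelled severe. Sections 7.1 and 7.8.3 also tie severe anaphylaxis to Appendix 3. The home paragraph carries no such cross-reference, so applying that meaning there is an inference, though a well-supported one.

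2. **What each instruction does with the event.**

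| Place | Action for this event | Stage 3 exception in the text? |
|---|---|---|
| 6.7.6 stop rule | Stop; nonresponder | This is the rule |
| 6.3.2 | Discuss and discontinue | Agrees with the rule |
| 4.3.1, if Grade 3 or 4 criteria are met | Terminate exposure | Agrees with the rule |
| 6.7.6 Home, counting clause | Counts as one use; a first use alone means a two-level reduction | None |
| 6.7.6 Home, observed dose | Clinic dose before home dosing resumes | None |
| 6.7.3.1 | Next dose in clinic the day after | None |
| 6.7.5.1, reached through 6.7.5.2 | Discontinuation left to discussion | None |

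3. **Whether the counting clause can operate.** If severe means stage 3, the subject has already stopped and there is no later use to add to the count. The clause is then inert, and misleading because a count presumes further dosing. If it means severe reactions below stage 3, it does have work to do. Such reactions exist: 6.7.1 lists stridor as a severe symptom, while Appendix 3 places it in stage 2. The clause does not say which it means.

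4. **Whether the epinephrine limits catch the case.** They do not. The general rule in 6.7.6 halts dosing after more than two doses for one reaction, and the list in 7.10.2 requires three or more. One injection meets neither.

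5. **Whether both can be followed.** Taken literally, the next-day dose in 6.7.3.1 and the stop in 6.7.6 cannot both be carried out for this subject. The stop rule is unqualified as to time and place, and 6.3.2 and 4.3.1 support it. It prevails, although the protocol nowhere states an order of precedence.

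6. **Frequency.** The documents give no rate for this event. Section 1.6.1 reports that 0% of AR101 subjects in ARC001 had a severe symptom (29 subjects were assigned to AR101). It anticipates severe, life-threatening serious anaphylaxis due to OIT in fewer than 0.5% of subjects. Neither figure is specific to stage 3 events at home.

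**The case against.** The best defence is that the outcome is already settled. The stop rule sits in the same section as the home paragraph and covers every setting, so a careful site would apply it. The observed-dose sentence can be read as fixing an order, clinic before home, for subjects who are allowed to resume; it does not decide who may. Counting a use does not order a dose. Safeguards surround the event: the emergency department visit, investigator assessment under 6.7.5.2, Medical Monitor consultation under 6.7.5.1, 24-hour reporting under 7.8.3, the mandatory terminations in 4.3.1, and the duty in 6.7.5 to discontinue a subject whose health could be jeopardized. Figure 6-2, the dose-adjustment schematic, is not shown in the text available and may carry a stage 3 branch. Enrollment was complete at Amendment 4.

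Most of this stands, and it limits the point to wording. It does not supply the missing exception in 6.7.3.1, whose next-day dose is not conditional on being allowed to resume. Nor does it give the counting clause a clear purpose.

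A reader might infer that the protocol directs re-dosing after stage 3 anaphylaxis, or that it contradicts itself beyond resolution. The documents do not support either reading, because the stop rule prevails. A reader might also infer a threat to the efficacy result, since SAP 7.4.1 classifies responders by the Exit DBPCFC and a subject wrongly kept on treatment could reach it. That would require a site to breach the stop rule, and the documents offer no basis for expecting it in any number.

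**Conclusion.** The point holds as a minor safety-wording inconsistency of low probability. The stage 3 stop rule governs. Three dosing instructions (6.7.6 Home, 6.7.3.1 and 6.7.5.1) do not defer to it, and the counting clause in the home paragraph is either inert or unclear. The planned primary analysis, the power and the SAP are not affected, and no number of affected subjects can be derived. That most doses are taken at home shows where the text applies; it says nothing about risk.

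The conclusion assumes that severe anaphylaxis in the home paragraph carries its Appendix 3 meaning, and that Figure 6-2 does not already resolve the matter. If the clause was meant for severe reactions below stage 3, it needs rewording instead of deletion; the other gaps remain.

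**What to change.** - In Epinephrine - Home, add a sentence: stage 3 anaphylaxis (Appendix 3) after a home dose ends dosing under the 6.7.6 stop rule, and the subject is a nonresponder.
- Limit the observed-dose sentence there, the next-day dose in 6.7.3.1 and the continuation option in 6.7.5.1 to reactions below stage 3 that do not meet the termination criteria in 4.3.1.
- Delete the counting clause, or reword it to name severe reactions below stage 3. Deletion is simpler, because a reworded clause must also agree with the Grade 3 criterion in 4.3.1.
- Check that Figure 6-2 agrees, and send sites a clarification letter.
- Section 3.4 says that former placebo subjects up-dose in ARC004 by the ARC003 procedures. If that protocol, which is not among the documents, repeats the wording, correct it there too.

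The cost is a few lines of protocol text and one letter. No new data and no SAP change are needed.
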